14.4 Missing, unused & spurious data

Participants with incomplete follow-up will enter the primary time-to-event analysis as right-censored observations. Further detail will be provided in the Statistical Analysis Plan (SAP).

14.5 Procedures for reporting deviation(s) from the original SAP

These will be submitted as substantial amendments where applicable and recorded in subsequent versions of the protocol and SAP.

14.6 Termination of the trial

Progression criteria for the internal pilot phase are described in Section 9.12. There is the potential for the trial to terminate early if our funder assesses the trial as not being feasible following the assessment of progress against our targets at the end of the internal pilot with input from our TSC and IDMC.

14.7 Inclusion in analysis

All randomised participants with non-zero follow-up time will be included in the primary intention-to-treat analysis. As part of sensitivity analyses, ineligible participants will be excluded from the analysis, and alternative analysis populations (as described in Section 15.1) will be used.

15 Analysis

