15.1 Main analysis

The final analysis will be performed after the end of the trial follow-up period, which is 48 months after the start of recruitment. Baseline demographic and clinical characteristics will be summarised descriptively by arm.

The primary analysis will be an intention to treat (ITT), including all randomised participants with non-zero follow-up time.

For the composite primary outcome (time from randomisation to the first occurrence of any element of the composite), a two-level Cox proportional hazards regression model will be fitted to estimate hazard ratios, including fixed effects for allocation and random effects to model heterogeneity between sites. Participants are censored at the end of the planned follow-up period (36 months), at

the end of the trial follow-up period, or (in case of dropout) at the time of their last follow-up, whichever occurs first. Regression analysis results will be presented as point estimates with confidence intervals and p-values from a log-rank test, and Kaplan-Meier curves of cumulative event rates at 36 months (31,32) will be generated to compare arms over time.

Primary estimand

Primary outcome question: In patients following endovascular intervention for CLTI, what is the event-free survival time of the three commonly used antithrombotic regimens (clopidogrel; aspirin plus clopidogrel; aspirin plus low-dose rivaroxaban), for those with a non-zero follow-up time?

The primary estimand is described by the following attributes:

- Population: Adults who are first time in CLARITY trial undergoing percutaneous or hybrid endovascular intervention for CLTI of the lower limbs, with atherosclerosis as the cause of CLTI, and with non-zero follow-up time.
- **Endpoint**: The clinical effectiveness endpoint is a composite event-free survival time examined over the trial duration. These events included acute limb ischaemia, major lower limb amputation, myocardial infarction, ischaemic stroke, and all-cause mortality. Participants are censored at the end of the planned follow-up period (36 months), at the end of the trial follow-up period, or (in case of dropout) at the time of their last follow-up, whichever occurs first.
- **Treatment condition**: Clopidogrel, aspirin plus clopidogrel, and aspirin plus low-dose rivaroxaban, regardless of discontinuation or initiation of the antithrombotic regimens.

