- Remaining intercurrent events: Death is incorporated into the clinical effectiveness primary outcome. Treatment discontinuation is covered by the previous attribute.
- Population-level summary: Hazard ratios, including fixed effects for allocation and random
 effects to model heterogeneity between sites. Regression analysis results will be presented as
 point estimates with confidence intervals and p-values from a log-rank test, and Kaplan-Meier
 curves of cumulative event rates at 36 months (31,32) will be generated to compare arms over
 time.

The primary safety outcome analysis will also use a two-level Cox regression as described above but include only those participants who received at least one dose of their allocated medication ('ontreatment' population). This analysis will include safety events that occurred after receiving the first dose of the trial medication and within 5 days after receiving the last dose.

Secondary outcomes will also be analysed based on ITT (for effectiveness outcomes) or 'on- treatment' populations (for safety outcomes) and using appropriate two-level regression models depending on the type of outcome: Cox regression for time-to-event outcomes, linear regression for continuous outcomes such as QoL measures (allowing for repeated measures where appropriate), and logistic regression for binary outcomes such as reintervention rates.

Table 7. Planned outcome analysis

Outcome	Measure	Analysis	Time frame	
Composite primary	Acute limb ischaemia	Two-level Cox regression		
outcome - Composite event-	Major lower limb amputation	Two-level Cox regression	2m, 6m, 12m,	
free survival time of the following:	Myocardial infarction	Two-level Cox regression	24m and 36m	
the following:	Ischaemic stroke	Two-level Cox regression		

Outcome	Measure	Analysis	Time frame		
	All-cause mortality	Two-level Cox regression			
Primary safety outcome	Major bleeding (ISTH definition)	Two-level Cox regression	2m, 6m, 12m, 24m and 36m		
	MALE (defined as amputation or any major reintervention)	Two-level Cox regression	2m, 6m, 12m, 24m and 36m		
	MACE (defined as recurrent CLTI, amputation affecting contralateral limb, acute coronary syndrome, ischaemic stroke)	Two-level Cox regression			
Caracilar	Major bleeding (BARC definition)	Two-level Cox regression			
Secondary outcomes	Major bleeding (TIMI definition)	Two-level Cox regression			
	Minor bleeding	Two-level Cox regression			
	Primary patency of artery	Two-level logistic regression			

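### The primary intention-to-treat set and the estimand population are conditioned on non-zero follow-up time, so they are not all randomised participants

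*Protocol*

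**What the plan says.** The condition stands four times in the current protocol: once in section 14.7 and three times in section 15.1.

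- Analysis set, 14.7: "All randomised participants with non-zero follow-up time will be included in the primary intention-to-treat analysis".
- Analysis set, 15.1: "The primary analysis will be an intention to treat (ITT), including all randomised participants with non-zero follow-up time".
- Estimand question, 15.1: the question is put "for those with a non-zero follow-up time".
- Estimand population, 15.1: adults having the procedure, "with atherosclerosis as the cause of CLTI, and with non-zero follow-up time".

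Section 15.1 also sets the terms against which the condition has to be read. The endpoint is "time from randomisation to the first occurrence of any element of the composite". Dropouts are censored "or (in case of dropout) at the time of their last follow-up, whichever occurs first". The treatment condition applies "regardless of discontinuation or initiation of the antithrombotic regimens". On intercurrent events it says: "Death is incorporated into the clinical effectiveness primary outcome".

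The protocol does not define how follow-up time is counted: date difference, date difference plus one, or clock time. The sensitivity analyses in 14.7 and 15.1 drop ineligible participants or use on-treatment, as-treated and per-protocol sets. None of them restores participants with zero follow-up.

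**The concern.** An estimand population should describe patients as they stand at entry. Whether a participant has any follow-up is settled only after allocation. Selecting on it means that the comparison is no longer between the groups as randomised, although the analysis is called intention-to-treat.

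The condition also sits badly with the rest of the estimand. The treatment condition ignores whether the regimen is started or stopped, and death counts as an outcome. Yet a participant who dies on the day of randomisation, or leaves at once, can fall outside the population.

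Two design features make this more than a matter of form. First, sections 9.2 and 9.5.2 allow randomisation on the day of the procedure. Second, the trial is open-label and section 10.1 lists withdrawal from randomisation to trial medication as an option, so very early withdrawal could differ by arm. The documents do not show that it will.

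**Working it through.** **Inputs (protocol 14.3).** 12-month event-free survival 65.0% on clopidogrel alone; hazard ratio 0.65; two-sided alpha 2.5% per comparison; power 90%; 387 events (157 + 115 + 115); 413 participants per arm, 1239 in total; dropout 8% per year; recruitment 25%, 35% and 40% over three years.

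**1. Reproduce the plan's figure.**
- Hazard ratio: ln(0.756)/ln(0.65) = 0.649, which agrees with 0.65.
- Events per comparison, Schoenfeld: 4(2.241 + 1.282)²/(ln 0.65)² = 268. Freedman: (1.65/0.35)²(2.241 + 1.282)² = 276. The stated 157 + 115 = 272 lies between them.
- With exponential survival and dropout, and observation ending 36 months after recruitment starts, 413 per arm give 157.0, 114.3 and 114.3 events, 385.6 in all. The stated 387 is reproduced on that basis. The day-of-randomisation count below uses only the hazards and the number randomised, not the length of follow-up.

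**2. Events expected on the day of randomisation.** The planned yearly hazards are −ln(0.65) = 0.4308 on clopidogrel alone and 0.65 × 0.4308 = 0.2800 on each combination.
- Clopidogrel alone: 413 × (1 − exp(−0.4308/365.25)) = 0.487.
- Each combination arm: 413 × (1 − exp(−0.2800/365.25)) = 0.316.
- Total: 0.487 + 2 × 0.316 = 1.12 events, and 1.12/387 = 0.3%.

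This is an upper figure at the planned constant hazard. It counts a whole day at risk and all five components of the composite.

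**3. Effect on power.** Power is Φ(|ln 0.65| × √D/2 − 2.241). At D = 272 it is 90.5%. Removing 0.487 + 0.316 = 0.80 events leaves 271.2 and gives 90.4%.

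**4. Effect on the hazard ratio of one lost event.** Scaling by event counts, a loss in a combination arm gives 0.65 × 114/115 = 0.644. A loss in the clopidogrel arm gives 0.65 × 157/156 = 0.654. The shift is about 0.004 to 0.006.

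**5. Participants with zero time and no event.** Someone censored at time zero is in no risk set for any later event, so leaving that person out does not change the Cox estimate. The number could still be noticeable. If last follow-up means the last trial contact (an assumption), those lost before the 2-month contact may have zero time: 1239 × (1 − 0.92^(2/12)) = about 17.

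**6. Where the definition travels.** Section 15.1 uses intention-to-treat for secondary effectiveness outcomes, including linear and logistic models. Section 15.3 imputes missing cost and EQ-5D-5L data on the intention-to-treat population for the base case. The only definition given is the restricted one. If it applies there, it changes who is analysed and imputed.

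**The case against.** The strongest reply is that the exclusion is on follow-up time, not on time to event. A participant with a non-fatal limb or cardiac event on the day of randomisation is still followed under section 12.2, and section 15.1 plans recurrent-event models, so such a person has non-zero follow-up. On that reading only a same-day death is at risk. This largely stands. Section 11.4 speaks of outcome events truncating the patient in the trial, which supports the other reading, so the text is ambiguous on non-fatal events.

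It is also fair that a plus-one or clock-time count would keep every same-day event, and that the coding of same-day times is ordinary analysis-plan content. What is not left to that plan is the condition itself, which the protocol writes into its primary set and estimand.

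A reader might infer two stronger things. The first is that the protocol definitely deletes events on the day of randomisation. It does not say so, because loss depends on an undefined count. The second is that several events are at stake because risk is raised just after the procedure. A hazard 5 or 10 times the average on that day would mean 5.6 or 11.2 events, but no such multiplier has a source in the documents, and randomisation may fall up to 10 days after the procedure. Even at 10 times, pairwise power would fall only to 89.6%.

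Nor does the protocol conceal the restriction: the qualifier is in the same sentence as the intention-to-treat label.

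**Conclusion.** The point holds as a fault of definition with a very small expected numerical effect. The primary set and the estimand population depend on a quantity observed after randomisation, and the intention-to-treat label is therefore not accurate. That conclusion needs no assumption about how time is counted.

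Loss of outcome events is conditional. A same-day death can be excluded if time is a date difference; a same-day non-fatal event can be excluded only if, in addition, follow-up ends at the first event. At the planned constant hazard this is at most about 1 of 387 events, with negligible change in power. Event-free participants with zero time leave the hazard ratio unchanged. Their exclusion matters for the description of the trial population and, if the definition is reused, for the secondary and cost-utility analyses.

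**What to change.** In sections 14.7 and 15.1:

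- Define the primary set as all randomised participants, analysed as allocated.
- Delete the non-zero follow-up condition from the estimand question and the population attribute.
- State that same-day events receive a positive time, for example date difference plus one day for everyone. Adding a constant to all times keeps their order.
- Report the number of participants with no follow-up by arm.

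This means editing the four places where the condition stands and adding one line on time counting and one on reporting. It changes neither the sample size nor trial conduct, and is best done before any unblinded analysis.

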15.1 Main analysis

The final analysis will be performed after the end of the trial follow-up period, which is 48 months after the start of recruitment. Baseline demographic and clinical characteristics will be summarised descriptively by arm.

The primary analysis will be an intention to treat (ITT), including all randomised participants with non-zero follow-up time.

For the composite primary outcome (time from randomisation to the first occurrence of any element of the composite), a two-level Cox proportional hazards regression model will be fitted to estimate hazard ratios, including fixed effects for allocation and random effects to model heterogeneity between sites. Participants are censored at the end of the planned follow-up period (36 months), at

the end of the trial follow-up period, or (in case of dropout) at the time of their last follow-up, whichever occurs first. Regression analysis results will be presented as point estimates with confidence intervals and p-values from a log-rank test, and Kaplan-Meier curves of cumulative event rates at 36 months (31,32) will be generated to compare arms over time.

Primary estimand

Primary outcome question: In patients following endovascular intervention for CLTI, what is the event-free survival time of the three commonly used antithrombotic regimens (clopidogrel; aspirin plus clopidogrel; aspirin plus low-dose rivaroxaban), for those with a non-zero follow-up time?

The primary estimand is described by the following attributes:

- Population: Adults who are first time in CLARITY trial undergoing percutaneous or hybrid endovascular intervention for CLTI of the lower limbs, with atherosclerosis as the cause of CLTI, and with non-zero follow-up time.
- **Endpoint**: The clinical effectiveness endpoint is a composite event-free survival time examined over the trial duration. These events included acute limb ischaemia, major lower limb amputation, myocardial infarction, ischaemic stroke, and all-cause mortality. Participants are censored at the end of the planned follow-up period (36 months), at the end of the trial follow-up period, or (in case of dropout) at the time of their last follow-up, whichever occurs first.
- **Treatment condition**: Clopidogrel, aspirin plus clopidogrel, and aspirin plus low-dose rivaroxaban, regardless of discontinuation or initiation of the antithrombotic regimens.
- Remaining intercurrent events: Death is incorporated into the clinical effectiveness primary outcome. Treatment discontinuation is covered by the previous attribute.
- Population-level summary: Hazard ratios, including fixed effects for allocation and random
 effects to model heterogeneity between sites. Regression analysis results will be presented as
 point estimates with confidence intervals and p-values from a log-rank test, and Kaplan-Meier
 curves of cumulative event rates at 36 months (31,32) will be generated to compare arms over
 time.

The primary safety outcome analysis will also use a two-level Cox regression as described above but include only those participants who received at least one dose of their allocated medication ('ontreatment' population). This analysis will include safety events that occurred after receiving the first dose of the trial medication and within 5 days after receiving the last dose.

Secondary outcomes will also be analysed based on ITT (for effectiveness outcomes) or 'on- treatment' populations (for safety outcomes) and using appropriate two-level regression models depending on the type of outcome: Cox regression for time-to-event outcomes, linear regression for continuous outcomes such as QoL measures (allowing for repeated measures where appropriate), and logistic regression for binary outcomes such as reintervention rates.

Table 7. Planned outcome analysis

Outcome	Measure	Analysis	Time frame	
Composite primary	Acute limb ischaemia	Two-level Cox regression		
outcome - Composite event-	Major lower limb amputation	Two-level Cox regression	2m, 6m, 12m,	
free survival time of the following:	Myocardial infarction	Two-level Cox regression	24m and 36m	
the following:	Ischaemic stroke	Two-level Cox regression		

Outcome	Measure	Analysis	Time frame		
	All-cause mortality	Two-level Cox regression			
Primary safety outcome	Major bleeding (ISTH definition)	Two-level Cox regression	2m, 6m, 12m, 24m and 36m		
	MALE (defined as amputation or any major reintervention)	Two-level Cox regression	2m, 6m, 12m, 24m and 36m		
	MACE (defined as recurrent CLTI, amputation affecting contralateral limb, acute coronary syndrome, ischaemic stroke)	Two-level Cox regression			
Caracilar	Major bleeding (BARC definition)	Two-level Cox regression			
Secondary outcomes	Major bleeding (TIMI definition)	Two-level Cox regression			
	Minor bleeding	Two-level Cox regression			
	Primary patency of artery	Two-level logistic regression			
	Secondary patency of artery	Two-level logistic regression			
	Reintervention	Two-level logistic regression			
	Healing of tissue loss	Two-level logistic regression			
	VascuQoL-6	Two-level linear regression	Baseline, 2m, 6m,		
	EQ-5D-5L	Two-level linear regression	12m, 24m and 36m		
	MALE using other major definitions	Two-level Cox regression	2m, 6m, 12m,		
Tertiary outcomes	MACE using other major definitions	Two-level Cox regression	- 24m and 36m		
	Complications from trial medications	Two-level logistic regression	Baseline, 2m, 6m, 12m, 24m and 36m		

The components of the composite primary outcome will also be analysed individually; for this, we will use competing risk models with all-cause mortality being a competing risk for other non-fatal outcomes. We will also explore the use of recurrent event models to reflect that patients may experience more than one outcome event and/or the same event multiple times (38,39). The distribution of different types of events over time will be visualised using e.g. swimmer plots.

In additional secondary analyses, we will calculate win statistics such as the win ratio or win odds to more directly express the probability of one treatment being better than the other, or being the best (40,41). We will also estimate and compare proportions of primary outcome events (as a composite and also each component individually) at 12 and 24 months, respectively.

We will consider the impact of different types of intercurrent events such as the timing of starting trial medication, discontinuing the prescribed medication, crossing over between arms, or using non-trial medication. To this end, sensitivity analyses will be performed using the 'on-treatment' population (for effectiveness outcomes) as well as other meaningful analysis populations e.g., based on the medication actually received ('as-treated') or including only those who fully adhered to their allocated

regimen ('per-protocol'). These will be specified in detail in the SAP using the estimands framework (40). Additional adjusted analysis incorporating important covariates, as well as potential subgroup analyses, will be specified in the SAP with stakeholder and PPI input (41). Variables likely to be considered include arterial territory (such as femoropopliteal or tibial), devices used during the intervention such as drug-eluting technology and diabetes.

If key assumptions such as proportional hazards do not hold, we will try alternatives such as accelerated failure time models or adding a stratification variable or time-varying covariate. To assess potentially informative censoring and non-compliance, an inverse probability-of-censoring weighted analysis will be undertaken.

A comprehensive SAP will be finalised by the trial statistician, with support from the TMG, agreed by the TSC, and signed off prior to any analysis being conducted. Results will be reported in line with the Consolidated Standards of Reporting Trials (CONSORT) statement and its extensions to multi-arm (42) and adaptive designs (43).

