14.1 Randomisation

Within 10 days of the endovascular procedure being performed, participants will be individually allocated in a 1:1:1 ratio to one of the initial three trial arms: (1) clopidogrel alone, (2) aspirin plus clopidogrel or (3) aspirin plus low-dose rivaroxaban for up to 36 months. Covariate-adaptive randomisation will be used to minimise the imbalance of key covariates with a random element apply to reduce the risk of subversion. These key covariates are:

- target artery (including iliac plus common femoral endarterectomy, iliac plus femoropopliteal, femoropopliteal, femoropoplital plus tibial, tibial, Iliac and tibial, hybrid with common femoral endarterectomy)
- trial site
- antiplatelet loading at the time of procedure (yes/no)

If one arm is dropped due to futility after the interim analysis (see Section 15.1.1.), the randomisation ratio will be adjusted to 1:1 between the two remaining arms.

The randomisation procedure will be implemented via a web-based remote system (available 24 hours a day) with telephone back-up as described in Section 9.5.2. Full details will be provided in a separate randomisation protocol.

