14.3 Sample size

We aim to recruit 1239 participants over 36 months and follow them up for a maximum of 36 months if recruited earlier in the trial, or a minimum of 12 months if recruited later. Assuming a 12-month event-free survival rate of 65.0% in the clopidogrel alone arm; an increase to 75.6% in at least one of the intervention arms, corresponding to a hazard ratio of 0.65 (10,11,14,35), a dropout/loss to follow-up rate of 8%/year (unpublished BASIL 3 data); a two-group log-rank test of equal exponential survival with a two-sided alpha of 2.5% (accounting for the three-arm design) and 90% power requires 387 primary outcome events (157 expected in the clopidogrel alone arm, 115 in each of the combination arms) to be observed (BASIL 3 data provided by Chief Investigator). Given the 36-month recruitment period (assuming 25%, 35% and 40% recruitment in the first, second and third year, respectively) and a maximum follow-up period of 36 months, this translates into 413 participants per arm, or 1239 in total (calculated with ART version 1.1.0 using Stata version 17.0) (36,37).

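### The primary model omits two of the three factors used to balance allocation, and the p-value comes from a different analysis than the hazard ratio

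*Protocol*

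**What the plan says.** **Allocation.** Protocol section 14.1: "Covariate-adaptive randomisation will be used to minimise the imbalance of key covariates". The factors are target artery (seven categories), trial site and antiplatelet loading (yes/no), with a random element. Section 9.5.2 names the same three.

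**Primary model.** Section 15.1 specifies a two-level Cox model, "including fixed effects for allocation and random effects to model heterogeneity between sites". The population-level summary of the primary estimand, in the same section, repeats this. Neither place mentions target artery or loading.

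**Test.** Results are to be given as "point estimates with confidence intervals and p-values from a log-rank test". No stratification of that test is stated.

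**Covariates.** Later in section 15.1, an additional adjusted analysis is left to the SAP. Arterial territory is among the variables likely to be considered; antiplatelet loading is not named.

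**Decision rule.** Section 15.1.1 tests each combination arm against clopidogrel at 2.5%, and compares the two combination arms with each other, at 5%, only if both are significantly better.

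**The concern.** Two separate things are at stake.

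1. **Estimate and test do not belong together.** The hazard ratio and interval come from a Cox model that allows for site. The log-rank p-value, as written, uses none of the three balancing factors. With a hard limit at 2.5%, and a further comparison that depends on passing it, a borderline result could show an interval on one side of the limit and a p-value on the other. The protocol does not say which decides. This holds whatever the prognostic strength of the factors.

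2. **The analysis does not follow the allocation.** Balancing arms on a prognostic factor reduces the chance variation of the treatment comparison. An analysis that ignores the factor does not credit that reduction, so its test tends to reject too seldom under the null and loses some power. A Cox hazard ratio that does not condition on such factors also lies nearer to 1 than one that does. Both effects vanish if the factors are not prognostic, so the size has to be worked out.

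**Working it through.** **Step 1: the plan's own figures.** Section 14.3 uses "a two-group log-rank test of equal exponential survival with a two-sided alpha of 2.5" (per cent), hazard ratio 0.65, and states that "90% power requires 387 primary outcome events", with "157 expected in the clopidogrel alone arm, 115 in each of the combination arms". That is 157 + 115 = 272 per comparison with clopidogrel.

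- Schoenfeld: 4(z₀.₉₈₇₅ + z₀.₉₀)² / (ln 0.65)² = 4(2.2414 + 1.2816)² / 0.1856 = 268 events.
- Freedman: (2.2414 + 1.2816)² × (1.65/0.35)² = 276 events.
- Power at 272 events: Φ(√272/2 × 0.4308 − 2.2414) = Φ(1.311) = 90.5%.

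Events per arm follow from N × λ/(λ+μ) × [1 − mean exp(−(λ+μ)F)], where F is follow-up time. The protocol's inputs are 65.0% event-free at 12 months on clopidogrel (λ = −ln 0.65 = 0.4308 per year; 0.65 × 0.4308 = 0.2800 in a combination arm), 8% annual dropout (μ = 0.08), accrual of 25/35/40% and N = 413. With follow-up stopped at 36 calendar months:

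- clopidogrel: 413 × 0.8434 × (1 − 0.5482) = 157.4
- each combination arm: 413 × 0.7778 × (1 − 0.6432) = 114.6

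The total is 386.6, so the stated 387 is reproduced.

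Section 15.1 instead places the final analysis 48 months after recruitment starts, with individual follow-up capped at 36 months. The same formula then gives 229.7 + 2 × 172.7 = 575 events, about 402 per pair and about 98% power. That difference needs its own reconciliation; here it only means that both timelines are examined.

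**Step 2: cost of omitting the factors.** The protocol gives no prognostic strengths, so four levels were assumed and simulated. Each run had 1,239 participants, minimised 1:1:1 on seven artery levels, loading and 20 sites (best arm chosen with assumed probability 0.8). Control 12-month event-free survival was calibrated to 65%, with two-sided 2.5% tests per pair. There were 4,000 null runs (about 307 to 314 events per pair) and 3,000 runs at hazard ratio 0.65 (about 270). The Monte Carlo standard error is about 0.25 points for type I error and 0.55 for power. The site effect was fitted by penalised partial likelihood. All analyses used the same simulated data.

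Strength is given as hazard ratio across artery levels / hazard ratio for loading / SD of site log hazard. Cells show planned model (Cox + site) against the model that adds artery and loading.

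| Assumed strength | Type I error, % | Power, % | Mean HR | Log-rank: type I, power, % |
|---|---|---|---|---|
| None (1 / 1 / 0) | 2.57 vs 2.60 | 89.2 vs 89.3 | 0.649 vs 0.647 | 2.55, 89.2 |
| Weak (1.5 / 1.2 / 0.15) | 2.70 vs 2.90 | 89.9 vs 90.2 | 0.650 vs 0.647 | 2.72, 89.6 |
| Moderate (2 / 1.5 / 0.20) | 2.62 vs 2.85 | 88.9 vs 89.9 | 0.654 vs 0.647 | 2.65, 88.9 |
| Strong (4 / 2 / 0.30) | 2.03 vs 2.48 | 86.6 vs 90.0 | 0.665 vs 0.646 | 2.03, 85.8 |

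Power lost: 0.1, 0.3, 1.0 and 3.4 points.

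**Step 3: the 48-month timeline.** In 1,500 runs of the strong case (about 389 events per pair), power was 95.3% against 97.1%, a loss of 1.8 points.

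**Step 4: p-value against interval.** In the strong case the log-rank test rejected in 85.77% of runs and the planned Cox model in 86.63%. They therefore gave different verdicts on the same data in at least 86.63 − 85.77 = 0.86% of runs. A net difference is only a lower bound on disagreement.

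**The case against.** The strongest reply is that the cost depends on something the protocol does not state. With weak or moderate factors the planned model's type I error was 2.70% and 2.62%, so no conservatism was visible, and the power loss was at most about one point. A clear effect needs a fourfold hazard range across artery levels and a twofold one for loading. Any error is on the conservative side and leaves type I control intact. The adjusted model's own type I error of 2.85% to 2.90% in two scenarios is within about 1.6 standard errors of nominal. All of this stands, and it is why the size is given as a range starting at zero.

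It can also be said that stratification of the log-rank test and choice of covariates are SAP matters. This stands only in part. A SAP could name strata, but the test would still be a different analysis from a Cox model with a site random effect. The primary model itself is fixed in the protocol, and covariates are assigned to an additional analysis. That analysis may cover artery, but it does not alter the primary one.

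Three stronger readings are tempting and not supported:

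- **That the hazard ratio is biased towards 1.** The shift (0.665 against 0.646 in the strong case) is non-collapsibility. A hazard ratio not conditional on artery and loading answers a different question from a conditional one.
- **That the quality-of-life models ignore the baseline score.** Table 7 lists baseline among the time points for both instruments and section 15.1 allows for repeated measures. How baseline enters is a detail for the SAP.
- **That the same covariates belong in every secondary model.** Some outcomes, such as TIMI major bleeding, may have few events, and nothing in the protocol shows that the models would support them.

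**Conclusion.** The point holds as a recommended improvement and not as a threat to validity. Two facts rest on the text alone: the primary Cox model omits two of the three balancing factors, and the p-value is taken from a different analysis than the hazard ratio and interval.

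The power cost is conditional: negligible to about 1 point for none to moderate prognostic strength, and about 3.4 points for strong factors on the event numbers of section 14.3 (1.8 points on the 48-month timeline). Deflation of the type I error appeared only in the strong case, where 2.03% lies about two standard errors below 2.5%. These figures rest on assumed prognostic strengths, site variation and minimisation probability. A reader might infer that the test is certainly conservative or the trial underpowered; the protocol supports neither.

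The case for change is that adjustment cost no measurable power when the factors were irrelevant (89.2% against 89.3%) and recovered it when they mattered.

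**What to change.** - In section 15.1, define the primary model as a Cox model with allocation, target artery and antiplatelet loading as fixed effects and site as a random effect. Seven artery categories may be sparse, so set a rule for collapsing them before unblinding.
- Take the hazard ratio, interval and p-value for each comparison from that model. Match the interval to the test level: 97.5% for each comparison with clopidogrel at 2.5%.
- Keep the log-rank test as supportive, and state that the model decides. Stratifying the log-rank test by site is a poorer remedy: in the simulation with no prognostic effects it had 88.0% power, against 89.2% unstratified.
- Amend the population-level summary of the primary estimand so that it names a hazard ratio conditional on these factors.

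The cost is wording in the protocol and SAP. Treated arteries and antiplatelet loading are already recorded at randomisation (Table 2, item 5), so no new data, participants or follow-up are needed.
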